1.6 Metformin in PAH

We have nearly completed an 8 week open label dose escalation (max dose 1g BID) study of metformin. Thus far we have enrolled 16 patients. There have been no serious adverse events thought related to the metformin exposure. One patient needed adjustment of diuretics and all patients have complained of mild diarrhea, with two requiring dose adjustment of metformin. Only one patient did not eventually reach the goal dose. In order to preserve the integrity of the study, we have not analyzed the primary endpoints aside from safety. In a preliminary review of MRS-quantified lipid content and found a numeric reduction in RV triglyceride content after treatment with metformin. These data suggest that RV lipid deposition may be reversed by metformin therapy and strongly support safety in a broad range of PAH patients with mild and severe disease.

Objectives and Specific Aims

1.7 Objectives

This is a phase II, 2x2 factorial randomized, blinded trial testing metformin versus placebo and a mHealth intervention (mHealth) versus usual care of 12 weeks. Specific Aims:

Primary Aim:

1. To determine whether a mHealth intervention, metformin, or both combined in PAH patients achieve the composite endpoint of 10% or greater improvement in six minute walk distance over baseline or improvement of at least one WHO functional class at week 12.

Secondary Aims:

1. To determine whether mHealth, metformin, or both interventions combined affects body weight at week 12.
2. To determine whether mHealth, metformin, or both interventions combined affects BMI at week 12.

3. To determine whether mHealth, metformin, or both interventions combined affects absolute 6MWD at week 12.
4. To determine whether mHealth, metformin, or both interventions combined affects Borg Dyspnea Score at week 12.
5. To determine whether mHealth, metformin, or both interventions combined affects emPHasis-10 quality of life survey score at week 12.
6. To determine whether mHealth, metformin, or both interventions combined affects WHO functional classification at week 12.
7. To determine whether mHealth, metformin, or both interventions combined affects average daily step count at week 12.
8. To determine whether mHealth, metformin, or both interventions combined affects frequency of daily goal attainment at week 12.
9. To determine whether mHealth, metformin, or both interventions combined affects daily aerobic time at week 12.
10. To determine whether mHealth, metformin, or both interventions combined affects total daily activity at week 12.
11. To determine whether mHealth, metformin, or both interventions combined affects resting heart rate at week 12.
12. To determine whether mHealth, metformin, or both interventions combined affects HOMA-IR at week 12.
13. To determine whether mHealth, metformin, or both interventions combined affects urine and plasma estradiol at week 12.
14. To determine whether mHealth, metformin, or both interventions combined affects urine and plasma estrogen metabolites at week 12.
15. To determine whether mHealth, metformin, or both interventions combined affects plasma lipid profiles at week 12.
16. To determine whether mHealth, metformin, or both interventions combined affects plasma free fatty acid profiles at week 12.
17. To determine whether mHealth, metformin, or both interventions combined affects plasma acylcarnitine profiles at week 12.
18. To determine whether mHealth, metformin, or both interventions combined affects plasma BNP at week 12.
19. To determine whether mHealth, metformin, or both interventions combined affects quadriceps skeletal muscle triglyceride content at week 12.
20. To determine whether mHealth, metformin, or both interventions combined affects change in quadriceps skeletal muscle fatigue at week 12.
21. To determine whether mHealth, metformin, or both interventions combined affects quadriceps skeletal muscle strength at week 12.

22. To determine whether mHealth, metformin, or both interventions combined affects quadriceps skeletal muscle contractile tissue cross-sectional area at week 12.
23. To determine whether mHealth, metformin, or both interventions combined affects RV myocardial muscle triglyceride content at week 12.
24. To determine whether mHealth, metformin, or both interventions combined affects tricuspid annular plane systolic excursion (TAPSE) at week 12.
25. To determine whether mHealth, metformin, or both interventions combined affects RV and LV ejection fraction at week 12.
26. To determine whether mHealth, metformin, or both interventions combined affects RV fractional area change at week 12.
27. To determine whether mHealth, metformin, or both interventions combined affects tricuspid annular velocity (S') at week 12.
28. To determine whether mHealth, metformin, or both interventions combined affects estimated RV and RA pressure at week 12.
29. To determine whether mHealth, metformin, or both interventions combined affects estimated RV and LV diastolic function at week 12.
30. To determine whether mHealth, metformin, or both interventions combined affects RV free wall longitudinal strain at week 12.
31. To determine screening clinical characteristics of responders and non-responders to mHealth, metformin, or both interventions combined at week 12.
32. To determine screening plasma metabolomics profiles, including all amino acids and lipidomics, of responders and non-responders to mHealth, metformin, or both interventions combined at week 12.
33. To determine whether metabolomics profiles and clinical features at screening predicts response to mHealth, metformin, or both interventions combined at week 12.
34. To determine whether change in metabolomics profile and clinical features from screening predicts response to mHealth, metformin, or both interventions combined at week 12.
35. To determine whether mHealth, metformin, or both interventions combined affects safety and tolerability in PAH subject over 12 weeks.
36. To determine fidelity of data collection and text transmission of mHealth, metformin, or both interventions over 12 weeks.
37. To determine patient satisfaction of mHealth, metformin, or both interventions at week 12.
38. To determine dropout rates of mHealth, metformin, or both interventions over 12 weeks.
39. To determine whether mHealth, metformin, or both interventions combined affects PAH-related hospitalizations over 12 weeks.

40. To determine whether mHealth, metformin, or both interventions combined affects medication regimen escalation/reduction over 12 weeks.
41. To determine whether mHealth, metformin, or both interventions combined affects incidence of death over 12 weeks.

Screening, Subject Selection, and Randomization

1.8 Recruitment of Study Sample

Patients will be recruited from the Center for Pulmonary Vascular Disease (CPVD) at Vanderbilt University Medical Center (Nashville, TN), the Pulmonary Hypertension Clinic at Mayo Clinic (Rochester, MN), and the Pulmonary Hypertension Program at Cleveland Clinic (Cleveland, OH). Study sites may be contacting, communicating, and recruiting participants by, 1) telephone, 2) email using their assigned institution email address or, 3) through a secure patient portal and associated electronic medical record.

Potentially eligible subjects will be pre-screened and informed about that study to determine if they have an interest in enrolling. After the initial pre-screening, the subject will provide in-person informed consent or e-consent before any study procedures are performed.

1.9 ResearchMatch.org will also be utilized as a recruitment tool for this protocol. ResearchMatch.org is a national electronic, web-based recruitment tool that was created through the Clinical & Translational Science Awards Consortium in 2009 and is maintained at Vanderbilt University as an IRB-approved data repository (see IRB #090207).Inclusion/Exclusion Criteria

Inclusion criteria:

- Adults aged 18 or older.
- Diagnosed with idiopathic, heritable, connective tissue disease – associated PAH, or drug- or toxin-associated pulmonary arterial hypertension (PAH) according to World Health Organization consensus recommendations.
- Repaired simple congenital heart disease or unrepaired ASD
- Stable PAH-specific medication regimen for three months prior to enrollment. Subjects with only a single diuretic adjustment in the prior three months will be included. Adjustments in IV prostacyclin for side effect management are allowed.
- Subjects must own a Bluetooth capable modern smartphone capable of receiving and sending text messages and an active data plan.
- FEV1 > or = 60% predicted and no more than mild abnormalities on lung imaging
- WHO Functional Class I-III
- Ambulatory

Exclusion criteria:

- Prohibited from normal activity due to wheelchair bound status, bed bound status, reliance on a cane/walker, activity-limiting angina, activity-limiting osteoarthritis, or other condition that limits activity.
- Pregnancy
- Diagnosis of PAH etiology other than idiopathic, heritable, connective tissue disease – associated PAH, or associated with drugs or toxins
- Drug and toxin associated PAH patients with active drug use
- WHO Functional class IV heart failure
- FEV1< 60% predicted with more than mild abnormalities on lung imaging
- Requirement of > 1 diuretic adjustment in the prior 30 days
- Preferred form of activity is not measured by an activity tracker (swimming, ice skating, stair master, or activities on wheels such as bicycling or rollerblading)
- Type I diabetes mellitus
- Prior diagnosis of cirrhosis
- Untreated hypo- or hyper-thyroidism
- eGFR by MDRD <40mL/min

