1.16 Metformin or Placebo

Subjects will receive metformin 500mg or equivalent placebo tablets via overnight shipment in adequate time for week 1. Patients will titrate the medication as follows: 1 Every Day x 5 days, 1 BID x 5 days, 1 TID x 5 days, and then 2 BID for the duration of the trial. This titration schedule is based on the excellent tolerability from our pilot study. Patients in the placebo group will have matching sugar pills prepared by the research pharmacy at Vanderbilt University Medical Center. Medication should be taken by participants all the way up to their Visit #2 date.

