1.19 Study Visits and Contacts

This study will consist of two visits: screening (-2 week) and week 12. The screening and week 12 visit are both estimated to take approximately 4-6 hours each. Patients will be consented by the PI, a clinical research coordinator, or a research nurse. Patient's written consent and study procedures will take place at the Pulmonary Vascular Disease Clinic (CPVD), the Clinical Research Center (CRC), and Vanderbilt Institute of Imaging Science (VUIIS) at Vanderbilt University Medical Center, Nashville, TN; the

Pulmonary Hypertension Clinic or the Clinical Research and Trials Unit (CRTU) at Mayo Clinic, Rochester, MN; and the Pulmonary Hypertension Program or Clinical Research Unit (CRU) at Cleveland Clinic, Cleveland, OH. There will be no changes to a patient's medication regimen.

Participants at Vanderbilt Medical Center will have the opportunity to participate in a sub study that includes a cardiac and skeletal MR spectroscopy, a noninvasive test measuring fat in the heart and skeletal muscles, and a muscle strength and function test at screening and week 12. The visits will occur at Vanderbilt Institute of Imaging Science (VUIIS). The MR spectroscopy will be performed by an experienced MRI technologist and be overseen by a faculty level imagining scientist.

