- To compare and define the screening plasma metabolomics profiles, including all amino acids and lipidomics, of responders and non-responders to mHealth intervention or no intervention and/or metformin at week 12.
- To assess the capacity of metabolomics profiles and clinical features at screening to predict response to the mHealth intervention or no intervention and/or metformin or placebo groups at week 12.
- To assess the capacity of change in metabolomics profile and clinical features from screening to predict response to the mHealth intervention or no intervention and/or metformin or placebo groups at week 12.
- To assess the effect of a mHealth intervention or no intervention and/or metformin or placebo on safety and tolerability in PAH subject over 12 weeks.
- To assess the fidelity of data collection and text transmission of a mHealth intervention over 12 weeks
- To assess the effect of a mHealth intervention or no intervention and/or metformin or placebo on patient satisfaction at week 12
- To assess the effect of a mHealth intervention or no intervention and/or metformin or placebo on dropout rates over 12 weeks.
- To assess the effect of a mHealth intervention or no intervention and/or metformin or placebo on PAH-related hospitalizations over 12 weeks.
- To assess the effect of a mHealth intervention or no intervention and/or metformin or placebo on medication regimen escalation/reduction over 12 weeks.
- To assess the effect of a mHealth intervention or no intervention and/or metformin or placebo on incidence of death over 12 weeks.

1.21.1 *Response to Therapy*

Response to therapy bot in will be classified as a binary yes or no response to therapy. A responder is defined by 10% or greater improvement in 6MWD over screening or improvement of at least one FC at week 12.

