1.33 Metformin

This drug has been on the market for several decades and is considered first line therapy for diabetes mellitus type 2. Moreover, it has been used extensively in non-hyperglycemic patients with polycystic ovarian disease. Additional studies of the safety of metformin in heart failure have been published. The pertinent risk of metformin is development of lactic acidosis. This risk has been reported primarily in patients with abnormal renal or hepatic function, thus we have chosen to exclude these populations from the study. Additional concerns include hypoglycemia, though this is a rare risk of this drug, and gastrointestinal distress. Patients will be educated on the signs and symptoms of hypoglycemia and advised to contact study staff immediately if any arise. Several other potential side effects listed in the package insert that will be monitored at

study visits and through phone conversation if need arises. We will monitor patients at baseline, week 1, week 3, week 6, week 9, week 12, week 15, and week 17 through either a visit or phone conversation. At these points, side effects that limit dose adjustment will be assessed. If patients report significant gastrointestinal effects, metformin will not be increased as would otherwise occur in the protocol. If symptoms persist further, the dose will be dropped by 500 mg daily to the highest tolerated dose.

The most common adverse reactions experienced are:

- >10% of patients: diarrhea (instant release tablet: 12% to 53%; extended release tablet: 10% to 17%), nausea/vomiting (instant release tablet: 7% to 26%; extended release tablet: 7% to 9%), flatulence (12%), Weakness (9%)
- 1% to 10%: chest discomfort, flushing, palpitation, headache (6%), chills, dizziness, lightheadedness, rash, hypoglycemia, Indigestion (7%), abdominal discomfort (6%), abdominal distention, abnormal stools, constipation, dyspepsia/heartburn, taste disorder, myalgia, dyspnea, upper respiratory tract infection, decreased vitamin B₁₂ levels (7%), increased diaphoresis, flu-like syndrome, nail disorder
- <1% (Limited to important or life-threatening): lactic acidosis, leukocytoclastic vasculitis, megaloblastic anemia, pneumonitis

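### Patients already taking metformin are neither excluded nor otherwise handled, so any who enrol would shrink the contrast in the metformin-containing primary comparisons

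*Combined protocol and SAP*

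**What the plan says.** The eligibility lists in the Protocol Summary and section 1.9 agree with each other. The one diabetes criterion is "Type I diabetes mellitus". Neither list mentions type 2 diabetes, metformin or any other glucose-lowering drug. The stability criterion is limited to PAH treatment, with an allowance for diuretics: "Stable PAH-specific medication regimen for three months prior to enrollment".

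Section 1.33 says that metformin "is considered first line therapy for diabetes mellitus type 2". Section 1.19 says of the patient's own drugs: "There will be no changes to a patient's medication regimen". Section 1.16 sends study tablets to every subject ("Subjects will receive metformin 500mg or equivalent placebo tablets via overnight shipment in adequate time for week 1") and titrates them on one schedule, ending "1 TID x 5 days, and then 2 BID for the duration of the trial", with no provision for someone who already has a metformin prescription.

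The primary endpoint is a change from screening: "A responder is defined by 10% or greater improvement in 6MWD over screening or improvement of at least one FC at week 12". Medications are reviewed at screening, at the telephone calls and at week 12 (sections 1.19.1, 1.19.3, 1.19.4 and Table 2), but no rule follows from finding metformin. Randomization is stratified by WHO functional class only (section 1.10). The covariates named in section 1.24 are baseline 6MWD, functional status, age and site. The one major violation specified in section 1.25 is not wearing the accelerometer.

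**The concern.** The trial tests metformin against no metformin, and the sample size assumes the full contrast. The protocol leaves eligible the group of diabetic patients for whom it calls the study drug first-line, and the Abstract describes glucose intolerance as common in PAH. Read literally, the text would admit a patient with type 2 diabetes who takes metformin and would keep that prescription going.

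Allocated to placebo, such a subject takes metformin throughout. Allocated to metformin, the subject takes study tablets in addition to the prescribed drug, and screening 6MWD and functional class were already measured under metformin. In both cases the subject contributes less than the assumed contrast. Two of the three primary comparisons in section 1.24 contain metformin, and the HOMA-IR, lipid and RV triglyceride comparisons are exposed in the same way. The sample size has no spare power to absorb a loss.

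**Working it through.** **Inputs from section 1.26.** Response is 40% on placebo and 73% on active treatment (0.40 + 0.50 − 0.17 = 0.73), with type I error 0.05, power 80% and 35 completers per group. Sidedness is not stated; two-sided is used because it reproduces the plan's 35.

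**Reproducing the plan's figure.** With a pooled variance and no continuity correction, the mean rate is (0.40 + 0.73)/2 = 0.565, and

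n = [1.960 × √(2 × 0.565 × 0.435) + 0.842 × √(0.40 × 0.60 + 0.73 × 0.27)]² / 0.33² = 34.2, rounded up to 35.

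This matches the plan. Normal-approximation power at 35 per group is 80.9%. Full enumeration of both binomial distributions with the Pearson chi-square test gives 79.8%, the reference value below.

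**Assumptions that the documents do not supply.**
- f: the share of randomized subjects already on metformin, taken as 5% to 20% in both arms.
- h: the fraction of the 33-point effect that study metformin still produces in an existing user, taken as 0 (no added effect) or 0.5 (half).
- Existing users on placebo respond at the placebo rate of 40%. This is reasonable for a change-from-screening endpoint in someone on the drug at both visits.

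**Formula.** Metformin-arm response = 0.73 − 0.33 × f × (1 − h); placebo stays at 0.40. For example, f = 0.10 and h = 0 gives 0.73 − 0.033 = 0.697, a difference of 29.7 points.

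| Share of users f | Difference, h = 0 | Exact power, h = 0 | Difference, h = 0.5 | Exact power, h = 0.5 |
|---|---|---|---|---|
| 0% | 33.0 points | 79.8% | 33.0 points | 79.8% |
| 5% | 31.4 | 75.0% | 32.2 | 77.5% |
| 10% | 29.7 | 69.8% | 31.4 | 75.0% |
| 15% | 28.1 | 64.2% | 30.5 | 72.5% |
| 20% | 26.4 | 58.5% | 29.7 | 69.8% |

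With h = 0, restoring 80% power by the plan's own formula would need 39, 43, 49 or 55 per group at 5%, 10%, 15% or 20% users.

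**A check on which arm is diluted.** Suppose instead that placebo-arm users respond at 73% and the metformin arm stays at 73%. The placebo rate becomes 0.40 + 0.33 × f, and exact power is 75.8%, 71.4%, 66.7% and 61.7%. The loss is of similar size. The two routes are alternatives and should not be added: doing so would suppose that background metformin produces a new response in one arm and none in the other.

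**Scope.** The table is for metformin versus placebo. In the combination arm an existing user still receives the mHealth intervention, so only the metformin part of that contrast shrinks. Section 1.26 puts the combination rate only above 73%, so its loss cannot be computed. In exercise versus placebo neither arm receives study metformin, so this route does not dilute it.

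**The case against.** The strongest reply is that this is a possibility and not a finding. A reader might infer that metformin users have been enrolled. The documents give no count or prevalence, so they support only the statement that such patients would not be kept out. That part of the reply stands, and every power figure is conditional on an assumed share.

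A reader might also infer that some subjects in the metformin arm get no new treatment. Section 1.16 contradicts this: everyone assigned to metformin receives titrated study tablets. What shrinks is the increment over existing treatment, and its effect is unknown, not zero. The h = 0 column is therefore the pessimistic case, which is why the half-effect column stands beside it.

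Third, the comparison remains randomized. Type I error is unaffected, and the trial still estimates the effect of adding study metformin to usual treatment. Section 1.27 describes a phase II trial that is useful even if null. This also stands: the harm is lost contrast and power, not an invalid test.

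Finally, a reader might infer that the titration and tolerability text assumes study tablets are a subject's only metformin. Sections 1.16 and 1.33 do not say so. The supportable point is narrower: sections 1.16 and 1.19 together leave unclear what happens to a subject with prescribed metformin.

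The reply does not remove the gap. No stratification factor, named covariate, per-protocol rule or medication-review step deals with these subjects.

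**Conclusion.** The concern holds as a conditional one. The protocol neither excludes nor otherwise handles current metformin users, and any who enrol would shrink the metformin part of two of the three primary comparisons. For metformin versus placebo, exact power falls from 79.8% to between 75.0% and 58.5% if 5% to 20% of subjects are users and study metformin adds nothing in them, or to between 77.5% and 69.8% if half the effect remains. These figures rest on the plan's 40% and 73%, on 35 per group, and on assumed values for the share of users and the retained effect, neither of which the documents fix. The documents do not support a claim of bias, of inflated type I error, or of untreated subjects in the metformin arm. This is a cheap improvement, not a flaw that must be repaired before the trial can be interpreted.

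**What to change.** 1. Add current metformin use at screening, or use within a look-back that the sponsor sets, to the exclusion list in both the Protocol Summary and section 1.9. Check it at the eligibility confirmation that sections 1.19.1 and 1.19.2 already require before randomization.
2. For anyone already randomized while on metformin, prespecify in section 1.24 a sensitivity analysis of the two metformin-containing comparisons with and without these subjects. The full randomized set stays primary. The subset is defined at baseline and can be identified from the screening medication review, so this remains possible even if enrolment has finished.
3. Reconcile sections 1.16 and 1.19 for any subject with prescribed metformin. How is a clinical matter for the sponsor.

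The cost is one eligibility line in an amendment and one extra analysis. The drawback is that a few patients with type 2 diabetes become ineligible, which slows accrual slightly in a rare disease.
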